3. STUDY DESIGN

A placebo-controlled multi-center adaptive randomized controlled trial, see figure 2 for the logistics of the study.

Figure 2: Study design of the trial

a. Duration of Follow-Up

The duration of follow-up for each participant depends on the interim results of the primary endpoint and the probability of obtaining a result, with a maximum of 168 days. The end of the study is defined as the last patient's last registration in the mobile application. Study participants will collect fingerstick dried blood spot (DBS) samples for serology testing at baseline, weeks 4, 8, 12, 16, 20 and 24. If they develop symptoms, they will be qPCR tested by nasopharyngeal swab, oral swab and/ or fecal swabs.

[figure not shown]

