6. STUDY PARAMETERS/ENDPOINTS

a. Primary study endpoint

Incidence of rt-PCR-confirmed SARS-CoV2 infection following BCG vaccination compared to that following placebo.

b. Secondary study endpoint

In individuals who test positive for Covid-19, the proportion with severe disease following BCG vaccination compared to placebo, as defined by the following necessary care levels: non-hospital care; patient hospitalized but no oxygen required; hospitalized and oxygen required; patient treated in intensive care and/or on mechanical ventilation; patient died.

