Data to be collected during follow-up includes intermittent surveys about the presence of flu-like symptoms, rt-PCR test results if done, serological test results, if testing positive for Covid-19 information regarding their disease course, and disease outcome status.

The following procedures will be performed and/or data collected as listed below data after informed consent is obtained:

Data Variable	
Date of signed Informed Consent Form	X
Role in hospital	X
Department in hospital	X
rt-PCR test for SARS-CoV2 result	X
Serological test for Covid-19 result	X
Number of BCG scars (by visual examination)	X
Medical history*	X
Previous PPD and IGRA test results	X
History of TB disease	X
History of previous HIV testing	X
Urine Pregnancy test result (if applicable)	X
Plans of pregnancy in 30 days	X
Plan to stop working in 3 months/ leave facility in 6 months	X
Current diabetes mellitus	X
Current chronic kidney disease	X
Currently taking immunosuppressive drugs	X

Living with someone with HIV, immunocompromised, taking immunosuppressive drug	X
Chemotherapy in past 3 months	X
History of organ/bone marrow transplant	X
Access to smartphone	X

b. Baseline data collection/procedures

The following procedures will be conducted and data collected as indicated below:

A questionnaire to obtain information about age, sex, demographic information, who they live with, smoking status, any current medications they are on, and other comorbidities

Participants will then be randomized to either receive a single dose of BCG vaccination or placebo.

BCG vaccination or placebo will be administered.

Eligibility screening data will carry forward into the trial.

The following additional data points will be collected:

Data Variable	
Age	X
Sex	X
Race	X
Ethnicity	X
Nationality	X
Who they live with	X
Height	X
Weight	X
Smoking status/tobacco use	X
Alcohol use	X
Current list of medications	X
Current list of comorbidities	X
History of diabetes mellitus	X
History of hypertension	X
History of stroke	X
History of kidney disease	X
History of COPD	X
Randomization assignment	X
BCG/placebo administered	X

c. Follow-up procedures and data collection:

Participants will be followed to assess whether they get infected with SARS-CoV2:

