Participants will complete intermittent surveys via an electronic system every 7 days to assess the presence of any flu-like symptom, including sore throat, fever, headache, malaise, and cough. Note that this is part of routine surveillance for Covid-19 in health workers at the United States site. Consent forms will ask for consent to access this survey information.

Any positive response on the survey will trigger a nasopharyngeal, oral and/ or rectal swab to be collected to test for Covid-19 via rt-PCR

All participants, regardless of survey responses, will have serology for Covid-19 tested at 4 week intervals during the follow-up period (6 months)

If a participant completes the follow-up period and does not test positive for disease, their study participation is complete

If a participant does test positive for disease, their disease status will be ascertained for up to two months or until an outcome is available through one of the following mechanisms: (1) an electronic survey if they are not admitted to the hospital, including questions about the number of days they are ill, daily fever, and other symptoms; or (2) if they are admitted to the hospital, ordinal outcomes for disease severity will be extracted from the hospital's electronic medical records system.

During the first week of follow-up, all participants will actively be asked about any adverse events; thereafter, participants will report unsolicited AEs through the electronic survey. Vaccine related adverse events will be graded using the FDA guidance (<https://www.fda.gov/media/73679/download>) and noted using WHO-recommended Adverse event following Immunization forms (AEFI; <https://vaccine-safety-training.org/classification-of-aefis.html>).

Participants will have the option of donating 12 mL of blood for plasma (serology) and PBMCs for secondary analysis of immune correlates and for future analysis based on covid19-specific IgM and IgG. If they do not donate 12mL of blood, a fingerstick will be required for baseline COVID19 serology.

Dried Blood Spot (DBS): all participants will self-collect DBS samples at week 4, 8, 12, 16, 20 and 24. Envelopes to store the DBS are provided upon enrollment and can be mailed or dropped off at work and picked up by study coordinators.

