10. SAMPLE SIZE AND STATISTICAL ANALYSIS

Data will be reported quantitatively. All analyses will be performed from the intention-to-treat principle. Missing data will be dealt with by multiple imputation using the mice package in R.

a. Sample size calculation

The study in the United States will include at least three sites: Houston (BCM and MD Anderson Cancer Center considered as 'one site' due to proximity), Texas A&M University (TAMU), and Cedars Sinai Medical Center (CSMC). TAMU will enroll 1400 individuals. The proposed enrollment sample size is designed to provide 80% power to detect a 60% vaccine efficacy (a relative risk of 0.4 among the vaccinated). This is based on the observed three-fold decline in respiratory infections in the South Africa adolescent cohort with 80% power and 0.05 type 1 error in a two-tailed test. We expect 5% of study participants to develop symptomatic COVID19 during follow-up, therefore a sample size of 1400, with 700 receiving intervention and 700 receiving placebo. We do not expect significant loss to follow up among HCWs (there has been zero LTF after the first 500 participants). We will plot Kaplan-Meier curves comparing COVID19 disease between the BCG and placebo groups and report hazard ratios and p-values using Cox proportional hazard models. DBS samples will be collected at baseline and weeks 4, 8, 12, 16, 20 and 24 post intervention. PBMCs and plasma donations are optional at baseline, 12 and 24 weeks. If interim analysis identifies a large proportion of participants to be seropositive before intervention, power analysis will be evaluated and an amendment will be submitted if additional participants need to be recruited.

b. Interim analysis

One month after the first 100 participants are enrolled, an interim analysis will be held by the independent statistician of the trial. Data will be exported independently from all sites and then data collated and merged for the interim analysis). The above described statistical analysis will be evaluated as well as safety profile. Enrollment is expected to occur within the first two months of launch. Interim analysis will occur based on study enrollment and three to six interim analysis will occur based on temporal dynamics of enrollment as requested by the DSMB. We will stop the clinical trial early if the p-value of any interim analysis is smaller than the pre-specified type-1 error cutoff. Each interim analyses will be reported to the DSMB.

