c. Primary study parameter(s)

The primary endpoint, development of COVID19 infection, we will use the Cox proportional-hazards model to calculate hazard ratios for the development of Covid-19. This will be reported as the proportion of individuals receiving the intervention who are PCR-positive or seroconvert.

d. Secondary study parameter(s)

Disease severity as discussed above and based on guidelines proposed by the World Health Organization. We will use the Chi square for significance to calculate the risk ratios for the development of severe Covid-19 disease. Disease severity will be based on the level of care required for individuals who test positive for COVID19 as follows: non-hospital-based care; patient hospitalized but no oxygen required; hospitalized and oxygen required; patient treated in intensive care and/or on mechanical ventilation; patient died. Additional WHO criteria for severity include severe pneumonia, respiratory failure, acute respiratory distress syndrome, sepsis and septic shock. Days absent will also be self-reported via the RedCap Research App. Immunology and epigenetic studies for innate training be implemented, but in brief, immune cells will be stimulated with non-specific (LPS, mitogen, BCG) and COVID19-specific antigens with immune function measured by ELISA and flow cytometry. Epigenetic studies are discussed in more detail below.

e. Other study parameters

Continuous baseline characteristics will be reported as mean and standard deviation or median and inter-quartile range, as appropriate. Categorical baseline characteristics will be reported as count and percentage. No statistical testing for baseline characteristics will be performed.

f. Synthesis

In this trial, the BCG vaccine will be used in hospital personnel during the epidemics to prevent infection with the new SARS-CoV-2 virus. The risk of the BCG vaccine is very well known (see product inserts) and only minor local side effects (redness, local pain) are common. The benefits of BCG vaccination based on earlier clinical studies are expected to be a reduction in infection and morbidity of at least 25% compared to unvaccinated individuals, and potentially much higher. These effects are mediated by the capacity of BCG to induce trained immunity and may represent an important tool for protection against SARS-CoV-2 virus infection until a specific effective vaccine is developed.

g. Epigenetic and Immune Corollary Studies

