COVID19 serology is currently being developed. When available (FDA approved test availability is rapidly evolving and improving), serology from blood drawn at baseline will be used to exclude individuals with preceding COVID19 infection from analysis.

To evaluate if the metabolic-epigenetic-immune mechanisms of the non-specific benefits of BCG for Covid19 are similar to that as previously described (Arts et al 2017), the collection of 12 mL of blood, in sodium heparin tubes, will be option to the participant. Blood will be processed for plasma (~4mL) and PBMCs. PBMCs will be cryopreserved and saved for future epigenetic (ATAC-seq, ChIP-seq, DNA methyl EPIC) and immune functional studies.

h. Flow cytometry based immune profiling

A secondary objective of this project is to elucidate the duration and immune correlate of protection of non-specific epigenetic-mediated immune “innate training” by BCG against Covid19. To do so, we will evaluate transcription regulation (DNA methylation, ATAC-seq, Chromatin immunoprecipitation), gene expression (reverse transcription PCR, RNA-seq) and immune phenotyping experiments (ELISAs) and multi-parameter immune phenotyping. We have developed multiple flow cytometry panels to measure the immune response. DNA methylation EPIC and other sequencing based arrays allow for genome wide evaluation of

epigenetic silencing. Genome wide evaluation will be validated with site-specific evaluation using PCR as previously described (DiNardo et al JCI 2020; 32125282). Flow cytometry-based immune phenotyping allows 18 parameters to simultaneously be measured. By first stimulating the PBMCs with viral or mycobacterial peptides, we are able to simultaneously **measure and correlate** the quantity and quality of the viral and/ or mycobacterial induced immune phenotype (CD4, CD8, CD36, CD14, CD23), transcriptional changes (T-bet, GATA-3, Foxp3, Helios) and functional immune response such as cytokine release (IL-2, IL-4, IL-10, TGF- β , TNF and IFN- γ) or effector function (perforin, CD107a). COVID19-specific viral peptide mixes are in development and the PBMCs will be saved for a time when measuring COVID19-specific immunity is feasible.

i. Epigenomic DNA methylation

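### A COVID-19-specific vaccine taken during follow-up is neither barred nor recorded, so the seroconversion rule in Section 10.c could count vaccine antibodies as infections

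*Combined protocol and SAP*

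**What the plan says.** The protocol describes the primary endpoint in two ways. Section 6.a gives "Incidence of rt-PCR-confirmed SARS-CoV2 infection following BCG vaccination compared to that following placebo". Section 10.c names a Cox model for the development of Covid-19 and continues: "This will be reported as the proportion of individuals receiving the intervention who are PCR-positive or seroconvert". It names no antigen and makes no exception for antibodies that come from vaccination.

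Follow-up is set in Section 3.a, "with a maximum of 168 days". Sections 3.a and 7.c collect dried blood spots for serology from everyone at weeks 4 to 24, every 4 weeks, whatever the symptom survey shows. On the assay, Section 10.g says "COVID19 serology is currently being developed". It plans to use baseline serology to exclude earlier infection from the analysis, but has no matching rule for antibodies that appear later for another reason.

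Section 10.f says that BCG "may represent an important tool for protection against SARS-CoV-2 virus infection until a specific effective vaccine is developed". The exclusion criteria in Section 4.c do not bar such a vaccine or entry into a trial of one. In Section 7.b, "Current list of medications" is a baseline item; the follow-up table in Section 7.c has no field for medication or vaccination. The opening of Section 10 says "All analyses will be performed from the intention-to-treat principle" and gives no censoring or intercurrent-event rule.

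**The concern.** A participant who received a specific vaccine would go on giving dried blood spots. If the assay detected the vaccine antigen, that person would turn seropositive and, under Section 10.c, become a primary event. The antibody would be real but would not come from infection.

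The planned number of events is small, so even modest uptake matters. Similar numbers of false events in both arms would dilute the risk ratio. Uptake need not be equal. Section 9.b says that almost all BCG recipients develop erythema and a small pustule, so some participants may guess their allocation. Detection need not be equal either: Section 11 reports higher antibody titres after influenza vaccination in people given BCG beforehand. Since receipt is not collected, the analysts would have no planned means of finding these events.

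**Working it through.** **Inputs.** From Section 10.a: 700 per arm, relative risk 0.4, two-sided 0.05, 80% power, 5% expected to develop symptomatic COVID19. Reading 5% as the placebo risk, the true risks are 5% and 0.05 × 0.4 = 2%, that is 35 v 14 events. Assumed, because the documents are silent: a share u of participants not otherwise infected takes a specific vaccine and seroconverts on the assay.

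**The plan's own figure.** For 5% v 2% at 80% power, the pooled two-proportion formula gives 588 per arm (1,176 in total), or 653 per arm (1,306) with continuity correction. The stated 1,400 is not reproduced but errs on the large side: power at 700 per arm is 86%. That is the reference below, and the discrepancy does not affect this point.

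**Dilution with equal uptake.** The counted risk in each arm is q = p + (1 − p)u, and apparent VE = 1 − q(BCG)/q(placebo). Power = Φ[(d − 1.96·se0)/se1], where d is the difference in counted risks, se0 its pooled and se1 its unpooled standard error.

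For u = 5%:
- placebo: 0.05 + 0.95 × 0.05 = 0.0975
- BCG: 0.02 + 0.98 × 0.05 = 0.069
- VE = 1 − 0.069/0.0975 = 29.2%
- d = 0.0285, se0 = 0.01477, se1 = 0.01475
- power = Φ[(0.0285 − 0.0289)/0.01475] = Φ(−0.03) = 49%

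| u | counted risk, placebo v BCG | events per arm | apparent VE | power |
|---|---|---|---|---|
| 0 | 5.0% v 2.0% | 35 v 14 | 60% | 86% |
| 2% | 6.9% v 4.0% | 48 v 28 | 43% | 68% |
| 5% | 9.8% v 6.9% | 68 v 48 | 29% | 49% |
| 10% | 14.5% v 11.8% | 102 v 83 | 19% | 32% |

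**Sensitivity to the base rate.** The 5% is a symptomatic rate. A composite that includes serology in everyone also counts asymptomatic infections, so its base rate should be higher.
- If 5% is the overall rate, the risks are 7.14% v 2.86%. Then u = 5% gives VE 34.5% and power 73%; u = 10% gives VE 23.5% and power 54%.
- If the risks are 10% v 4% (assumed), u = 5% gives 14.5% v 8.8%, RR 0.61, power 92%; u = 10% gives 19.0% v 13.6%, RR 0.72, power 78%.

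**Sensitivity to the assay** (5% v 2%). If it detects half of vaccinees, 10% uptake acts like u = 5% and VE is 29%. If it detects none, VE stays at 60%.

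**Unequal uptake** (5% v 2%, full detection).
- Placebo 10%, BCG 5%: 14.5% v 6.9%, VE 52%. If BCG does nothing: 14.5% v 9.75%, a spurious VE of 33%.
- Placebo 10%, BCG 15%: 14.5% v 16.7%, VE −15%.

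**The case against.** The strongest reply is that the false-event route needs three things, none of which the documents establish.

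1. A specific vaccine must be taken within the 168 days. Section 10.f mentions one only as something still to be developed, with no date. A reader might infer that the sponsor expects one during the trial; the text does not say so. All the dilution figures rest on an assumed uptake.
2. The assay must detect the vaccine antigen. Section 10.g names no assay or antigen. A reader might infer that the plan necessarily counts vaccine antibodies as infections; it only leaves that possible.
3. Section 10.c must prevail over Section 6.a. Under rt-PCR-confirmed infection alone, no antibody can be an event.

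The 5% v 2% figures also apply a symptomatic rate to a broader endpoint, so they sit towards the high end of the dilution. Recovery afterwards is not ruled out: consent covers access to medical records for medical history, participants are surveyed every 7 days, and the DSMB can ask for further data.

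All of this stands, and it limits how firmly the point can be put. It does not close the gap. None of those routes is planned to capture vaccination or can be relied on to do so. The unnamed assay and the two endpoint definitions leave the possibility open. Even under Section 6.a, unrecorded vaccination would mix a second preventive product into the BCG v placebo comparison.

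**Conclusion.** The gap is real and its consequence is conditional. As written, the plan could count vaccine antibodies as infections, and it collects nothing that would let the analysts identify those events reliably. With equal uptake the estimate moves towards no effect. At 5% v 2% and full detection, 2% to 10% uptake takes apparent VE from 60% to between 43% and 19%, and power from 86% to between 68% and 32%. At an assumed 10% v 4%, 10% uptake gives RR 0.72 with power about 78%. The false-event effect is nil under the rt-PCR-only endpoint or with an assay that separates infection from vaccination.

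Two stronger conclusions are tempting. One is that the bias must run towards no effect. That holds only for equal uptake and detection, and the visible BCG reaction and the influenza-titre finding leave room for either direction. The other is that the primary result is already compromised. That would need vaccine availability, assay antigen and endpoint precedence to be settled against the plan, and the documents settle none of them. The severity is therefore should-fix.

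**What to change.** 1. Add to the existing 7-day survey: receipt, product and date of any SARS-CoV-2 vaccine, and enrolment in another COVID-19 prevention trial.
2. Reconcile Sections 6.a and 10.c into one primary endpoint.
3. If serology stays in that endpoint, state in Section 10.c that seroconversion first detected after a specific vaccine does not count unless the assay separates infection from vaccination, while PCR-confirmed events still count.
4. Report one analysis that censors at vaccination and one intention-to-treat analysis that continues PCR-confirmed events past it, and name in advance which is primary.

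The cost is a few survey items and a short amendment. Some serological follow-up is lost. If uptake is uniform over 24 weeks and censoring is non-informative, expected events after censoring are 49 × (1 − u/2). At 10% uptake that is about 46.5 events, and power by the Schoenfeld formula falls from 89% to 88%; at 50% uptake it is about 36.8 events and 79%. The main downside is that censoring departs from intention to treat and may be informative if uptake differs by arm. That is why both analyses are needed.

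### Sections 6.a and 10.c disagree on whether serology counts as a primary event; if it does, seroconversion needs a definition and a confirmation rule, because unconfirmed positives over six tests could dilute the efficacy estimate

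*Combined protocol and SAP*

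**What the plan says.** Two sections define the primary event differently. Section 6.a (Primary study endpoint) takes it to be infection confirmed by rt-PCR and does not mention serology. Section 10.c (Primary study parameter(s)) sets out a Cox model and adds: "This will be reported as the proportion of individuals receiving the intervention who are PCR-positive or seroconvert".

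Section 7.c has everyone tested whether or not they report symptoms: participants "will have serology for Covid-19 tested at 4 week intervals during the follow-up period (6 months"). Sections 3.a and 10.a give the visits as baseline and weeks 4, 8, 12, 16, 20 and 24, which is six tests after baseline. The data table in Section 7.c instead lists serology every two weeks.

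On the assay, Section 10.g says "COVID19 serology is currently being developed". It adds that approved tests are improving, and that baseline serology will be used to exclude people with earlier infection from the analysis. The documents do not name the assay, cutoff or specificity, do not define seroconversion, and do not call for a repeat sample, second assay or PCR to confirm a positive.

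**The concern.** If a first positive after a negative baseline is an event, each uninfected participant has six chances of becoming a false case. The planned risk is low (5% in one arm, 2% in the other on the plan's effect size), so even a small error rate per test can add false events on the scale of the true ones. False events unrelated to treatment pull the hazard ratio toward 1. An effective vaccine could then be reported with too low an efficacy, or missed. Leaving the rule unwritten also lets the case definition be settled after data have been seen.

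**Working it through.** **Inputs from Section 10.a.** The design has "a sample size of 1400, with 700 receiving intervention and 700 receiving placebo", "with 80% power and 0.05 type 1 error in a two-tailed test", and targets "60% vaccine efficacy (a relative risk of 0.4 among the vaccinated"). On the event rate: "We expect 5% of study participants to develop symptomatic COVID19 during follow-up". I read this as 5% on placebo and 5% × 0.4 = 2% on BCG. On dropout: "We do not expect significant loss to follow up among HCWs", so none is allowed for.

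**Assumptions, because the documents give no figure.** Per-test specificity sp from 98% to 99.9%; errors independent between visits and equal in both arms; true cases all detected.

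**The plan's own figure.** The pooled two-proportion formula for 5% v 2% gives 588 per arm (1176 in total), or 653 per arm (1306) with continuity correction. So 1400 is not reproduced exactly but is on the safe side: power at 700 per arm is 86.4%. This difference does not bear on the point.

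**Dilution with a single unconfirmed positive.**
- Chance of at least one false positive over six tests: f = 1 − sp⁶.
- Observed risk in an arm with true risk p: p + (1 − p) f.
- Power = Φ{[√n |p₁ − p₂| − 1.96 √(2p̄(1 − p̄))] / √(p₁(1 − p₁) + p₂(1 − p₂))}, with n = 700.

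Example at 99%: f = 1 − 0.99⁶ = 0.0585. Placebo: 0.05 + 0.95 × 0.0585 = 0.1056. BCG: 0.02 + 0.98 × 0.0585 = 0.0773. RR = 0.0773 / 0.1056 = 0.73.

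| Specificity per test | f | False cases, placebo / BCG | Observed risks | RR | Power |
|---|---|---|---|---|---|
| 100% | 0 | 0 / 0 | 5.00% v 2.00% | 0.40 | 86% |
| 99.9% | 0.60% | 4 / 4 | 5.57% v 2.59% | 0.46 | 81% |
| 99.8% | 1.19% | 8 / 8 | 6.13% v 3.17% | 0.52 | 75% |
| 99.5% | 2.96% | 20 / 20 | 7.81% v 4.90% | 0.63 | 61% |
| 99% | 5.85% | 39 / 40 | 10.56% v 7.73% | 0.73 | 45% |
| 98% | 11.42% | 76 / 78 | 15.84% v 13.19% | 0.83 | 29% |

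The expected true cases are 700 × 5% = 35 and 700 × 2% = 14. The corresponding hazard ratios are close to the RRs: 0.46 at 99.9%, 0.62 at 99.5% and 0.72 at 99%.

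**Sensitivity to the assumptions.**
- Higher true risk, since serology also finds infection without symptoms. At an assumed 10% v 4%: RR 0.54 and power 96% at 99.5%; RR 0.63 and power 89% at 99%. At an assumed 7.5% v 3%: RR 0.57 and 85%; RR 0.67 and 72%.
- 5% read as the overall rate (7.1% v 2.9%): RR 0.68 and power 69% at 99%.
- Half of the false positives persistent and removed by the baseline exclusion (5% v 2%): RR 0.54 and power 72% at 99.5%, in place of 0.63 and 61%.
- Twelve tests, as the two-weekly table entry implies (5% v 2%): RR 0.73 and power 45% at 99.5%.

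**With confirmation.** Requiring two consecutive positives among the six independent tests gives 0.1, 0.4 and 1.4 false cases per arm at 99.5%, 99% and 98%. RR is 0.40, 0.41 and 0.42, and power 86%, 86% and 84%. If the rule misses 10% of true cases, the risks become 4.5% v 1.8% and power about 82%. If it misses 20%, they become 4.0% v 1.6% and power about 78%.

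**The case against.** The strongest reply is that Section 6.a governs. If the primary endpoint is rt-PCR-confirmed infection, serology adds no primary events and there is no dilution. That stands: the whole calculation depends on the Section 10.c wording. But Section 10.c is the analysis instruction for the primary endpoint, so one of the two sections has to change.

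A reader might infer that the plan instructs that a single positive counts. It does not; it is silent. One positive after a negative baseline is only the natural reading of an undefined term.

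The 5% rate is for symptomatic disease, whereas serology covers everyone. With more true infections the power loss shrinks or disappears, as the 10% v 4% case shows. The pull on the estimate remains: 0.63 where the truth is 0.40.

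The assay might also be very good. Section 10.g expects tests to improve, and Section 4.a has baseline blood banked with serologic status evaluated later, so a better assay may be available by then. At 99.9% the planned 80% power is still met. The baseline exclusion can remove people with stable cross-reactivity, so independence between visits overstates the build-up. It cannot remove false positives that first appear at a later visit.

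Finally, equal error in both arms is an assumption. Blinding and identical schedules support it, but Section 11.b reports that BCG raised antibody titers to an influenza vaccine, so a differential error cannot be excluded.

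**Conclusion.** The point holds in conditional form. The two definitions of the primary event must be reconciled. If serology counts, the case definition is incomplete, and the likely consequence is attenuation of the effect. Its size depends on a specificity the documents do not give: slight at 99.9% (RR 0.46, power 81%), serious at 99.5% (0.63, 61%) and at 99% (0.73, 45%), given 5% v 2%, 700 per arm, and errors independent between visits and equal between arms. Higher true infection risk protects power but not the estimate. Persistent cross-reactors caught at baseline make the effect smaller.

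Two stronger readings are not supported. One is that the trial is underpowered whatever assay is used; the 99.9% row and the higher-risk cases contradict it. The other is that the bias must be toward no effect; that needs equal error in both arms, which is assumed. The change is worth making as a cheap improvement to the case definition.

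**What to change.** First state in Sections 6.a and 10.c, in the same words, whether serology contributes to the primary endpoint, and settle the four-weekly or two-weekly schedule. If serology contributes:

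- Name the assay and cutoff, and give its specificity on dried blood spots once known.
- Define a serologic primary event as a negative baseline followed by a confirmed positive. Confirmation is a positive at the next scheduled sample, or a repeat positive on the stored sample with a second assay. The second route is needed at week 24 and is useful when the next sample is missed.
- Read samples blind to arm and date the event at the first positive.
- Report PCR-confirmed events separately.

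The cost is plan wording plus repeat assays on the positives, using samples already scheduled; the second-assay route assumes enough stored material. The downside is that some true seroconverters are missed through waning antibody or missed samples, leaving power at about 82% if 10% of cases are missed and about 78% if 20% are. With an assay as good as 99.9%, that loss could cancel the power gained, although the estimate would still be less diluted. If the two tests share the same cross-reactivity, the gain is smaller, which is the reason to prefer a different second assay.

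### The chi-square planned for severe disease is unreliable at the expected case counts: with no continuity rule stated, false harm is modestly too frequent and a borderline result depends on an unstated choice

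*Combined protocol and SAP*

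**What the plan says.** Section 10.d (Secondary study parameters) names the test: "We will use the Chi square for significance to calculate the risk ratios for the development of severe Covid-19 disease". Section 6.b defines the endpoint as "In individuals who test positive for Covid-19, the proportion with severe disease following BCG vaccination compared to placebo", so the denominator is infected participants, not everyone randomised. Section 10.d repeats this: "Disease severity will be based on the level of care required for individuals who test positive for COVID19 as follows", followed by five care levels. No cut-off for severe is given.

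Section 10.a supplies the inputs that fix the likely case counts: "We expect 5% of study participants to develop symptomatic COVID19 during follow-up", a relative risk of 0.4 on infection, and "a sample size of 1400, with 700 receiving intervention and 700 receiving placebo". It states "80% power and 0.05 type 1 error in a two-tailed test" for the sample size calculation. The secondary endpoint has no alpha of its own.

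The plan does not say whether the chi-square carries a continuity correction or what happens when cells are small. It gives no expected number of severe cases and no severe rate for trial participants.

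**The concern.** The chi-square relies on a large-sample approximation. Here it would be applied to a few dozen infected participants, of whom a handful may be severe. If the vaccine prevents infection as hypothesised, the two groups of cases are also unequal, about 1 to 2.5. With small and unequal groups the approximation can err more in one direction than the other, even when its total error looks acceptable.

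This is the only test named for the secondary objective, whether BCG lessens severity. A trial that succeeds on infection is the one that produces the imbalance, and so the one in which a couple of severe cases on BCG could be reported as significant harm.

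**Working it through.** **1. The plan's sample size.** For 5% v 2%, two-sided 0.05 and 80% power, the mean proportion is 0.035 and

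n per arm = [1.96 × √(2 × 0.035 × 0.965) + 0.8416 × √(0.05 × 0.95 + 0.02 × 0.98)]² / 0.03² = 588,

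or 653 with continuity correction. The stated 700 is not reproduced, but it is larger than its inputs need (power 86.4%, or 82.9% with continuity correction). I use 700 as given.

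**2. Expected cases.**
- 5% read as the placebo rate: placebo 700 × 0.05 = 35; BCG 35 × 0.4 = 14.
- 5% read as the overall rate: 1400 × 0.05 = 70, split 0.4 to 1, so 20 v 50.
- No effect on infection: 35 v 35.

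**3. Error rates at 14 v 35, no true effect on severity.** The severe rate is my assumption, because the documents give none for trial participants. Every 2 × 2 table was enumerated with binomial counts, and rejections at two-sided 0.05 (mid-p at one-sided 0.025) were split by direction. Nominal is 2.5% each way.

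| Severe rate (assumed) | Expected severe, BCG / placebo | Pearson: harm | Pearson: benefit | Yates: harm | Mid-p: harm |
|---|---|---|---|---|---|
| 5% | 0.7 / 1.75 | 3.6% | 0.0% | 0.6% | 0.7% |
| 10% | 1.4 / 3.5 | 3.8% | 0.1% | 1.1% | 1.3% |
| 15% | 2.1 / 5.25 | 3.5% | 0.7% | 1.1% | 1.8% |
| 20% | 2.8 / 7.0 | 3.3% | 1.4% | 1.3% | 2.1% |
| 30% | 4.2 / 10.5 | 2.8% | 1.9% | 1.5% | 2.2% |

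Pearson here is uncorrected. Its total two-sided error is 3.6% to 4.7% over these rates. The largest harm tail is 3.9%, at a severe rate of about 7.5%.

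**4. Other splits, uncorrected Pearson.**
- 20 v 50: harm 4.0% and benefit 0.0% at a 5% severe rate; 3.4% and 0.7% at 10%.
- 35 v 35: equal tails, 2.87% each at 10%, so 2 × 2.87% = 5.7% in total.
- 28 v 70 (twice the cases): 3.2% and 1.5% at 10%.

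**5. The smallest harm result, 2/14 v 0/35.**
- Pearson: 49 × (2 × 35 − 12 × 0)² / (14 × 35 × 2 × 47) = 240,100 / 46,060 = 5.21, p = 0.022.
- Yates: 49 × (70 − 24.5)² / 46,060 = 2.20, p = 0.138.
- Fisher: (14 × 13) / (49 × 48) = 0.077. Both severe cases on placebo is a more probable table, so nothing is added for the other tail.
- One-sided mid-p: half of 0.077 = 0.039, above 0.025.

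**6. The smallest benefit result with no severe case on BCG.** At 0/14 v 8/35, Pearson p = 0.051, Fisher p = 0.085 and one-sided mid-p = 0.026, so none rejects. At 0/14 v 9/35 they are 0.036, 0.045 and 0.017, so all three reject. The threshold is the same for all three.

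**The case against.** The strongest reply has four parts.

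- **The stated level holds.** The only level in the plan is two-tailed 0.05, and total error at 14 v 35 stays under it. Judging each direction at 2.5% is the reviewer's standard. This stands: overall alpha is not inflated at that split, and the fault is in how the error is divided.
- **Yates removes it.** The plan says only chi-square. With the correction no tail exceeds 2.5% and the 2/14 v 0/35 signal disappears. This also stands, but it supports specifying the test, since two readings of one sentence give p = 0.022 and p = 0.138.
- **The split and severe rate are assumed.** 14 v 35 needs 5% to be the placebo rate and 60% efficacy to be real. "TAMU will enroll 1400 individuals" is said of one of at least three sites, and section 10.c also counts seroconversion, so there could be more cases. At 28 v 70 the tails move closer together, and at a 30% severe rate the excess nearly vanishes.
- **No decision hangs on it.** The severity halting rule in section 9.d uses no p-value.

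A reader might also infer three stronger points that the documents do not support:

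- **That the chi-square makes benefit unreachable.** Fisher and mid-p need the same 0/14 v 9/35. Few cases and conditioning on infection set that limit.
- **That the same fault appears with all 700 per arm as denominator.** There the Pearson null tails are equal, at 1.8% to 2.3% each. A single table such as 4 v 0 (Pearson 0.045, Fisher 0.124) shows only that Fisher is the more conservative test.
- **That all five care levels would go into a 2 × 5 table.** Sections 6.b and 10.d speak of a proportion with, and risk ratios for, severe disease, which is a binary comparison.

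**Conclusion.** The point holds in a limited form. At the case counts implied by section 10.a, the chi-square in section 10.d is a poor choice and is under-specified. At 14 v 35 with a 5% to 15% severe rate, the uncorrected version gives false harm of 3.5% to 3.8% in place of 2.5%, and almost no false benefit. The excess persists at 20 v 50. At 35 v 35 the tails balance, but total error is 5.7% at a 10% severe rate.

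The size is modest and rests on three assumptions: no continuity correction, case numbers close to those in section 10.a, and a low severe rate, which the documents do not state. One conclusion does not depend on the severe rate: for 2/14 v 0/35, the reported result turns on a choice that the plan leaves open.

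**What to change.** In section 10.d, replace the chi-square with one named exact test, either Fisher mid-p or Boschloo, with each direction at one-sided 0.025. Report the risk ratio with an exact confidence interval. State the choice before unblinding.

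At 14 v 35, mid-p brings false harm to between 0.7% and 2.2% over severe rates of 5% to 30% and leaves the benefit threshold where it is. The cost is a change of SAP wording, a line of code and slightly conservative p-values. The change corrects the excess false-harm tail only and adds no power to show benefit on severity.
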